## **Restricted Mean Survival Time (RMST)**

The hazard ratio estimate from the Cox proportional hazard model is routinely used to empirically quantify the between-arm difference under the assumption that the ratio of the two hazard functions is constant over time. When this assumption is plausible, such a ratio estimate may capture the relative difference between two survival curves. However, the clinical meaning of such a ratio estimate is difficult, if not impossible, to interpret when the underlying PH assumption is violated (ie, the hazard ratio is not constant over time).

The RMST is a robust and clinically interpretable summary measure of the survival time distribution. Unlike median survival time, it is estimable even under heavy censoring. There is a considerable body of methodological research (eg, Royston and Parmar, 2011; Uno, Wei, et al., 2014; Zhang, 2013) about the use of RMST to estimate treatment effects as an alternative to the hazard ratio approach.

The RMST methodology is applicable independently of the PH assumption and can be used, at a minimum, as a sensitivity analysis to explore the robustness of the primary analysis results. However, when large departures from the PH assumption are observed, the log-rank test is underpowered to detect differences between the survival distributions for the treatment arms, and a test of the difference between the RMST for the experimental arm and the control arm may be more appropriate to determine superiority of the experimental arm compared to the control arm with respect to the time-to-event endpoint.

In particular, as it pertains to the **cut-off point ( $\tau$ )** to evaluate the RMST, it is noted that the cut-off point should not exceed the minimum of the largest observed time for both treatment arms so that the RMST of all treatment arms being evaluated can be adequately estimated and comparison between treatments is feasible;  $\tau$  should be clinically meaningful and closer to the end of the study follow-up so that the majority of survival outcomes will be covered by the time interval. The RMST up to time  $\tau$  can then be interpreted as the expected survival time restricted to the common follow-up time  $\tau$  among all patients. The selection of  $\tau$  should ensure that the RMST evaluation will not go beyond the maximum time point where the evaluation can be performed while also taking into account a large period of time that is expected to provide a meaningful assessment of treatment effect. To avoid arbitrary selection of the common cut-off  $\tau$  for both treatment arms, three sets of analyses will be performed:

- $\tau_1$  = minimum of (largest observed PFS time for the experimental arm, largest observed PFS time for the control arm).
- $\tau_2$  = minimum of (largest PFS event time for the experimental arm, largest PFS event time for the control arm).
- $\tau_3$  = midpoint between  $\tau_1$  and  $\tau_2$ .

The treatment effect between the experimental arm and the control arm will be assessed based on the difference in RMST. The associated 95% CI for the difference in means and 1-sided p-value will be generated.

## **Exploratory analyses to investigate the impact of potential prognostic or effect modifying (predictive) factors**

See subgroups as defined in Section 6.4.

Multivariable Cox regression analysis will be carried out to assess and adjust the treatment effect for relevant baseline factors of potential prognostic impact. A stepwise selection procedure will serve to identify explanatory variables of potential prognostic values additional to the randomization strata which will be included in all models during the selection procedure. The Cox's Proportional Hazard model is defined as:

$$h(t) = h(0;t) e^{Xb}$$

where  $h(0;t)$  defines the baseline hazard function and  $X$  defines the vector of explanatory variables and  $b$  the unknown vector of regression parameters.

In the stepwise selection procedure, variables are entered into and removed from the model in such a way that each forward selection step can be followed by one or more backward elimination steps. The stepwise selection process terminates if no further variable can be added to the model or if the variable just entered into the model is the only variable removed in the subsequent backward elimination. The level of significance for an explanatory variable to enter the model is set to 0.15 (p-value of Score test) and the significance level for removing it is set to 0.40 (p-value of Wald test). This analysis will be performed using the stepwise selection method in SAS (Proc PHREG). Once this procedure stops, the factor 'treatment arm' will be added to the last selected model in order to evaluate the effect of treatment on PFS time when adjusted for the selected explanatory variables. The hazard ratios of all selected explanatory variables and of treatment effects will be reported including 2-sided 95% CIs. No interactions will be considered. Post-baseline factors will not be considered for the model.

### **PFS per modified RECIST v1.1 vs PFS per standard RECIST v1.1**

Summaries of PFS assessment per modified RECIST v1.1 versus standard RECIST v1.1 will be provided including numbers of concordant and discordant assessments as well as the number of cases where PFS is determined to occur at different timepoints based on the censoring rules described in Table 13 (S0 based on programmatically derived investigator assessment or S0\_B based on BICR assessment).

Table 15 outlines the possible outcomes per modified RECIST v1.1 and standard RECIST v1.1, a similar classification used for possible outcomes of assessment by investigator and BICR (Amit O, et al., 2011).

**Table 15. Possible Outcomes per Modified RECIST v1.1 vs Standard RECIST v1.1**

		Standard RECIST v1.1	
		Event	No Event
Modified RECIST v1.1	Event	$a = a1 + a2 + a3$	b
	No Event	c	d

a1: number of agreements on timing and occurrence of event;

a2: number of times agreement on event but modified RECIST v1.1 declares event later than RECIST v1.1;

a3: number of times agreement on event but modified RECIST v1.1 declares event earlier than RECIST v1.1;

$N = a+b+c+d$ .

The timing agreement of event is defined with a window of 28 days

The following measure of discordance will be calculated for each treatment arm:

- Total Event Discrepancy Rate:  $(b+c) / N$
- Early Discrepancy Rate (EDR):  $(a3+b) / (a+b)$
- Late Discrepancy Rate (LDR):  $(a2+c) / (a2+a3+b+c)$
- Overall Discrepancy Rate:  $(a2+a3+b+c) / N$

The EDR represents the positive predictive value of modified RECIST v1.1 assessment and quantifies the frequency with which modified RECIST v1.1 will declare PFS event earlier than standard RECIST v1.1 within each arm as a proportion of the total number of modified RECIST v1.1 assessed PFS events.

The LDR quantifies the frequency with which modified RECIST v1.1 criteria assigns PFS event later than standard RECIST v1.1 criteria as a proportion of the total number of discrepancies within the treatment arm.

## Biopsy

The following will be listed and summarized by treatment arm.

Disease site, lesion number, clinical evaluation date and outcome, imaging evaluation date and outcome, whether biopsy was done, reason, date of biopsy sample and biopsy outcome, will be listed for each patient. Lesions evaluated after PD per modified RECIST v1.1 will be flagged in the listing.

In what follows, lesions evaluated from randomization until PD per modified RECIST v1.1 will be considered.

The number of times a lesion underwent clinical evaluation and/or underwent imaging evaluation will be summarized overall and by disease site.

For each clinical evaluation outcome and imaging evaluation outcome and for the combination of outcomes), the following will be summarized. The denominator to calculate percentages is the total number of lesions evaluations; all lesion evaluations are counted if the same lesion is evaluated at multiple visits.

- Number of lesion evaluations
- Number and percentage of biopsies performed, reason and outcome
- Number of and percentage of biopsies not performed and reason

The following cross tabulations will be provided. The denominator to calculate the percentages will be based on the total number of lesions evaluations; all lesion evaluations are counted if the same lesion is evaluated at multiple visits. Biopsy status and outcome will include all combination of categories for biopsy performed (yes, no), reason to perform or not perform, and outcome if performed (positive, negative, inconclusive)

- Clinical evaluation outcome vs. biopsy status and outcome
- Imaging evaluation outcome vs. biopsy status and outcome
- Combination of clinical and imaging outcome vs biopsy status and outcome
- Clinical evaluation outcome vs. imaging evaluation outcome.

#### **6.2.2.3. Sensitivity analyses for overall survival**

The following sensitivity analyses will be performed to explore the robustness of the primary analysis results for OS. These analyses are regarded as purely exploratory. The sensitivity analyses will repeat the primary analysis (p-value, HR and 95% CIs) described in Section 6.2.2.1 with the modifications below:

- PP analysis set;
- unstratified;
- using strata derived according to eCRF data instead of that entered in IRT.

#### **Methods for evaluating the validity of model assumptions**

The same methodology described in Section 6.2.2.2 for PFS will be used for OS.

#### **Exploratory analyses to investigate the impact of potential prognostic or effect modifying (predictive) factors**

The same methodology described in Section 6.2.2.2 for PFS will be used for OS.

#### **6.2.2.4. Locoregional failure**

Locoregional failure (LRF) is defined as locoregional PD per RECIST v1.1 with pathologic confirmation or locoregional clinically detectable progression with pathologic confirmation or salvage of primary tumor with tumor present on final pathology or salvage neck dissection >20 weeks after completion of CRT with tumor present on final pathology.

Time to LRF is defined as the time from the date of randomization to the date of the first documentation of locoregional PD per RECIST v1.1 with pathologic confirmation, locoregional clinically detectable progression with pathologic confirmation, salvage of primary tumor with tumor present on final pathology, salvage neck dissection >20 weeks after completion of CRT with tumor present on final pathology or death due to any cause, whichever occurs first.

Time to LRF data will be censored on the date of the last adequate tumor assessment or clinical evaluation for patients who do not have an event (LRF or death); the analysis will consider any LRF or death as an event regardless of the number of prior missing tumor assessments or clinical evaluations or timing of the event with respect to initiation of anti-cancer therapy.

The censoring and LRF event date options to be considered are presented in Table 16.

$$\text{LRF (months)} = [\text{date of event or censoring} - \text{date of randomization} + 1] / 30.4375$$

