### 3.2. Tumor Assessments

- Tumor assessments will be completed on the schedule detailed below using a modification of RECIST v1.1. The modification is required in head and neck cancer assessment as these tumors are fairly unique in their accessibility for thorough clinical evaluation and biopsy. Furthermore, the extensive mucosal surface which is available for clinical evaluation of tumor response or recurrence may indicate tumor status changes that may not be present or as clear on radiographic imaging alone. Conversely, radiographic changes that could be suggestive of tumor progression or recurrence can reflect radiation therapy changes. Taken collectively, this has given rise to the clinical practice of using biopsies to directly assess tumor recurrence in this patient population. Therefore, RECIST was modified for this protocol to recognize this practice and better confirm (through direct pathologic ascertainment) when tumor recurrence has occurred.
- Radiographic and clinical evaluations will be conducted with the same schedule in both treatment arms of the study. The investigator will assess antitumor activity based on radiological assessments and clinical evaluation of patients using modified RECIST v1.1 (see [Appendix 3](#)) at baseline, 12 weeks after the completion of CRT, every 16 weeks (Q16W) thereafter for 48 months (208 weeks), and every 24 weeks (Q24W) thereafter until confirmed disease progression per modified RECIST v1.1 and regardless of discontinuation of study treatment or initiation of subsequent anti-cancer therapy.
- Radiological tumor assessments will also be conducted whenever disease progression is suspected (eg, symptomatic deterioration or physical exam findings suggestive of mucosal recurrence).
- Locoregional disease progression per modified RECIST v1.1 requires that radiographic changes suggestive of disease progression are confirmed by biopsy. Pathologic confirmation of progression will verify that radiographic changes represent true tumor progression and not radiation effects or non-malignant contrast enhancement.
- When disease progression occurs for distant metastases per RECIST v1.1, confirmation of pathology is recommended unless medically contraindicated or if the lesion location is too high risk for biopsy.

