**Table 16. Outcome and Event Dates for Time to LRF Analysis**

Scenario	Date of event/censoring	Outcome
No adequate baseline assessment and no LRF and no death	Date of randomization	Censored
No adequate post-baseline tumor assessment or clinical evaluation and no death	Date of randomization	Censored
LRF or death	Date of LRF or death	Event
No LRF and no death	Date of last adequate tumor assessment or clinical evaluation documenting no LRF	Censored

The time to LRF in Arm A and Arm B will be compared based on the FAS using the strata assigned at randomization and using a 1-sided stratified log-rank test at 1-sided nominal alpha level of 0.025.

The treatment effect will be estimated using a Cox's Proportional Hazard model stratified by the randomization strata to calculate the hazard ratio. Each stratum will define a separate baseline hazard function (using the 'STRATA' statement in SAS PROC PHREG), ie, for the i-th stratum the hazard function is expressed as:  $h(i;t) = h(i,0;t) \exp(x\beta)$ , where  $h(i,0;t)$  defines the baseline hazard function for the i-th stratum and  $x$  defines the treatment arm (0=Arm B, 1= Arm A) and  $\beta$  is the unknown regression parameter.

Ties will be handled by replacing the proportional hazards model by the discrete logistic model (Ties=Discrete option in SAS PROC PHREG).

Kaplan-Meier estimates (product-limit estimates) will be presented by treatment arm together with a summary of associated statistics including the median LRF time with 2-sided 95% CIs. In particular, the LRF rates at 12, 24, 36, 48 and 60 months will be estimated with corresponding 2-sided 95% CIs. The CIs for the median will be calculated according to

Brookmeyer and Crowley (1982) and the CIs for the survival function estimates at the time points defined above will be derived using the log-log transformation according to Kalbfleisch and Prentice (2002) (conftype=loglog default option in SAS Proc LIFETEST) with back transformation to a CI on the untransformed scale. The estimate of the standard error will be computed using Greenwood’s formula.

Frequency (number and percentage) of patients with each event type (LRF or death) and censoring reasons will be presented by treatment arm.

Reasons for censoring will be summarized according to the categories in Table 17 following the hierarchy shown.

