**Table 17. Time to LRF Censoring Reasons and Hierarchy**

Hierarchy	Condition	Censoring Reason
1	No adequate baseline assessment AND no LRF AND no death	No adequate baseline assessment
2	No event and [withdrawal of consent date ≥ date of randomization OR End of study (EOS) = Patient refused further follow-up]	Withdrawal of consent
3	No event and lost to follow-up in any disposition page	Lost to follow-up
4	No event and [EOS present OR disposition page for any epoch after screening says patient will not continue into any subsequent phase of the study] and no adequate post-baseline assessment	No adequate post-baseline assessment
5	No event (no LRF AND no Death) AND Distant Metastatic (DM) failure	Distant Metastatic failure only
6	No event and none of the conditions in the prior hierarchy are met	Ongoing without an event

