#### 6.2.2.5. Distant metastatic failure

Distant metastatic failure or distant metastasis (DM) is defined as new tumor identified at a site distant from the head and neck anatomic region or draining lymph nodes.

Time to DM is defined as the time from the date of randomization to the date of the first documentation of metastatic disease progression per RECIST v1.1 or death due to any cause, whichever occurs first. DM data will be censored on the date of the last adequate tumor assessment or clinical evaluation for patients who do not have an event (DM or death); the analysis will consider any DM or death as an event regardless of the number of prior missing tumor assessments or clinical evaluations or timing of the event with respect to initiation of anti-cancer therapy.

The censoring and DM event date options to be considered are presented in Table 18.

$$DM \text{ (months)} = [\text{date of event or censoring} - \text{date of randomization} + 1] / 30.4375$$

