**Table 19. Time to DM Censoring Reasons and Hierarchy**

Hierarchy	Condition	Censoring Reason
1	No adequate baseline assessment AND no DM AND no death	No adequate baseline assessment
2	No event and [withdrawal of consent date $\geq$ date of randomization OR End of study (EOS) = Patient refused further follow-up]	Withdrawal of consent
3	No event and lost to follow-up in any disposition page	Lost to follow-up
4	No event and [EOS present OR disposition page for any epoch after screening says patient will not continue into any subsequent phase of the study] and no adequate post-baseline assessment	No adequate post-baseline assessment
5	No event (no DM AND no Death) AND Locoregional (LRF) failure	Locoregional failure only
6	No event and none of the conditions in the prior hierarchy are met	Ongoing without an event

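### The LRF and DM analyses count any death as failure and censor patients alive with failure only at the other site, so their tests, hazard ratios and rates do not isolate locoregional or distant control

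*SAP*

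**What the plan says.** SAP 6.2.2.4 defines LRF by four locoregional findings, each needing pathology. Time to LRF ends at the first of these, the last on the list being a late salvage neck dissection "with tumor present on final pathology or death due to any cause, whichever occurs first". The section adds that "the analysis will consider any LRF or death as an event regardless of the number of prior missing tumor assessments", and says the same about the start of other anti-cancer therapy. Under Table 16 a patient with neither LRF nor death is censored at the "Date of last adequate tumor assessment or clinical evaluation documenting no LRF". Table 17, fifth row, gives a separate censoring reason to the patient with "No event (no LRF AND no Death) AND Distant Metastatic (DM) failure".

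SAP 6.2.2.5 mirrors this. Time to DM ends at "the first documentation of metastatic disease progression per RECIST v1.1 or death due to any cause, whichever occurs first"; "the analysis will consider any DM or death as an event regardless of the number of prior missing tumor assessments"; and Table 19, fifth row, censors the patient with "No event (no DM AND no Death) AND Locoregional (LRF) failure".

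Both endpoints get a stratified log-rank test at nominal one-sided 0.025, a stratified Cox model, and Kaplan-Meier 'LRF rates' or 'DM rates' at 12 to 60 months. Protocol 9.3.2.5 and 9.3.2.6 define the same composites but plan only Kaplan-Meier summaries.

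Protocol 3.2 schedules tumor assessments "thereafter until confirmed disease progression per modified RECIST v1.1". Protocol 3.3 counts distant metastasis as PD. Under Protocol 3.1, survival follow-up continues after PD. Neither document plans a cause-specific or cumulative-incidence analysis of LRF or DM.

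**The concern.** Take two patients with distant metastasis at the same visit and no LRF. Scheduled imaging ends for both, while survival follow-up goes on. The one still alive at the data cut is censored for LRF at about the time of the metastasis. The one who dies becomes an LRF event at death. Time after the metastasis thus enters the LRF analysis mainly when it ends in death, and the death counts whatever its cause.

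Two things follow. First, a treatment that only prevents metastases, and so the deaths that follow them, moves the LRF curve. Second, the composite is itself estimated with one-sided use of follow-up. LRF and DM are listed as antitumor activity beside PFS and OS, and a reader will take an LRF hazard ratio with a small p-value as evidence of better locoregional control. The analysis as planned cannot support that statement by itself.

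**Working it through.** **Calibration.** The documents give no event number for LRF or DM, so the PFS design was reproduced first (Protocol 9.1: HR 0.68, 90% power, one-sided 0.025, 289 events).
- Schoenfeld: 4 × (1.960 + 1.282)² / (ln 0.68)² = 42.0 / 0.1487 = 283.
- Freedman: (1.68 / 0.32)² × (1.960 + 1.282)² = 27.56 × 10.51 = 290.

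Both are within 3% of 289.

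**Inputs from the documents.** 640 patients, 1:1 (Protocol 3.1). Control median PFS 33 months, so a total failure hazard of ln 2 / 33 = 0.0210 per month; control median OS 70 months; 22 months of accrual; 15% drop-out (Protocol 9.1). Final PFS analysis at 51 months (SAP Table 8, note).

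**Assumptions.** Constant cause-specific hazards; uniform accrual (the protocol says non-uniform); exponential drop-out over 51 months; unstratified log-rank test. Death without progression is 15% of first events and DM is 20%, 30% or 40%; the rest is LRF. Median survival after DM is 30 months (the value that reconciles median PFS 33 with median OS 70) or 10.1 months (upper figure for recurrent disease in Protocol 1.3). The drug acts on DM only; the true LRF hazard ratio is 1. There were 1,500 trials per scenario.

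**Result for LRF under the SAP rule** (hazard ratio; share of trials with one-sided p < 0.025):

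| DM share | Median survival after DM | DM HR 0.68 | DM HR 0.50 |
|---|---|---|---|
| 20% | 30 months | 0.977; 4.1% | 0.968; 4.4% |
| 20% | 10.1 months | 0.960; 5.3% | 0.937; 8.2% |
| 30% | 30 months | 0.963; 4.9% | 0.945; 7.1% |
| 30% | 10.1 months | 0.936; 8.4% | 0.900; 14.1% |
| 40% | 30 months | 0.946; 7.3% | 0.912; 9.9% |
| 40% | 10.1 months | 0.908; 12.5% | 0.855; 24.4% |

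- Cause-specific LRF test: 2.0% to 3.2% throughout, hazard ratio about 1.00. The simulation standard error at 2.5% is √(0.025 × 0.975 / 1500) = 0.4 points.
- No drug effect at all: the SAP test is significant in 2.1% to 2.3% of trials.
- Share of LRF events that are deaths: from (298 − 226) / 298 = 24% to (292 − 157) / 292 = 46%.
- Mirror case (drug acts only on LRF, HR 0.68, DM share 30%): DM hazard ratio 0.909 or 0.866, significant in 10.8% or 22.1% of trials; cause-specific DM test 2.5% or 2.2%.
- LRF after DM still recorded (DM share 30%, DM HR 0.50): 5.7% to 14.0%.
- Data cut at 90 months (same setting): 12.5% to 24.7%.

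**Plausibility of the shares.** With no drug effect, DM-first patients at 51 months number 68, 102 and 137 of 640 (11%, 16%, 21%), inside the 10% to 30% in Protocol 1.2.1. LRF-first patients number 222, 188 and 154 (35%, 29%, 24%) against 35% to 65% there, so the 20% DM share fits that second figure best.

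**A second split.** With first failures 50% LRF, 30% DM and 20% death, the LRF test is significant in about 5% to 10% of trials at DM HR 0.68 and 5% to 19% at 0.50, for mean survival after DM from 67 down to 8 months. The 67 comes from the design means: (70 / ln 2 − 33 / ln 2) / 0.80 = (101.0 − 47.6) / 0.80. At this split most of the effect comes from counting deaths. The one-sided use of follow-up after DM adds 0 to 3 percentage points to the significance probability and raises the composite's 36-month event estimate by up to about 3 points.

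**The case against.** The composites are stated openly in Protocol 9.3.2.5 and 9.3.2.6 and in SAP 3.2.2. If a drug prevents metastatic deaths, LRF-or-death truly improves, and rejecting that null is no error. The SAP also tabulates event types by arm, the patients censored with failure only at the other site, and every PD subtype (6.1.1.1), so a careful reader can see when deaths drive a difference. The upper end of the range needs a DM effect stronger than the design hazard ratio of 0.68 and short survival after DM; longer survival, as the PFS and OS medians imply, gives results near 4% to 10%.

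All of this stands. It limits the point to interpretation but does not remove it: the counts are descriptive, while the hazard ratio, p-value and curve still merge the components.

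Three stronger readings are tempting and not supported:
- A reader might infer that the plan overstates the incidence of locoregional failure. SAP 6.2.2.4 attaches survival-function confidence intervals to the LRF rates, so they are event-free probabilities of the composite, not incidences of LRF.
- A reader might infer an inflated false-positive rate. With no drug effect, the test of the stated composite stays at its nominal level.
- A reader might infer that the plan gives no information on where the drug acts. The tabulations give some.

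**Conclusion.** The LRF and DM tests, hazard ratios and Kaplan-Meier rates do not isolate site-specific control. At the 51-month cut, a drug that reduces only metastases gives a nominally significant LRF result in roughly 4% to 24% of trials (4% to 13% at DM HR 0.68; 4% to 24% at 0.50), with an apparent LRF hazard ratio of 0.98 to 0.86, against about 2% to 3% for a cause-specific test. The range rests on the assumed DM share, DM effect, survival after DM and constant hazards. Cumulative incidence was not simulated.

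It would be wrong to infer that the trial's main conclusions are at risk. Both endpoints are secondary, tested at a nominal level, and outside the sequence of PFS then OS in SAP 5.1.2. PFS, OS and their type I error are unaffected. This is a cheap improvement to secondary analyses, worth making before unblinding.

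**What to change.** In SAP 6.2.2.4 and 6.2.2.5:

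1. Keep the protocol composites but label the results locoregional-failure-free survival and distant-metastasis-free survival, including the rates at fixed times.
2. Add as supportive analyses, for LRF and DM as type of first failure: Aalen-Johansen cumulative incidence by arm, and a stratified cause-specific hazard ratio and log-rank test, with other-site failure and death as competing events. State how LRF and DM found at the same assessment are counted.
3. Base any statement about locoregional or distant control on these supportive analyses.

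The eCRF already records PD subtype, so no new data are needed; the work is SAP wording and standard software. The cost is one more estimand to report and explain. It describes first failures only, so LRF after DM, and the reverse, would lie outside it.
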